### **Cold Urticaria:**

The aim is to estimate the treatment effect of ligelizumab compared to placebo, for the target population on the primary endpoint (i.e. change from baseline to week 12 in CTT). The justification of the corresponding primary estimand is detailed in [Section 2.1](#).

The primary analysis method is based on a two-sample t-test.

The null hypothesis ( $H_0$ ) for the primary endpoint is that the change from baseline at Week 12 in CTT in any of the ligelizumab groups (low or high dose) is not superior to the placebo group:

$$H_{01.Cold}: \mu_{ligelizumab} \geq \mu_{Placebo} \text{ versus } H_{A1.Cold}: \mu_{ligelizumab} < \mu_{Placebo}$$

where  $\mu$  is the mean change from baseline of CTT at week 12, negative value indicates improvement.

### **Cholinergic Urticaria:**

The aim is to estimate the treatment effect of ligelizumab compared to placebo, for the target population on the primary endpoint (i.e. change from baseline to week 12 in itch NRS following the pulse-controlled ergometry test). The justification of the corresponding primary estimand is detailed in [Section 2.1](#).

The primary analysis method is based on a two-sample t-test.

The null hypothesis ( $H_0$ ) for the primary endpoint is that the change from baseline at Week 12 in itch NRS in the ligelizumab 120 mg q4w group is not superior to the placebo group:

$$H_{01.Chol}: \mu_{ligelizumab} \geq \mu_{Placebo} \text{ versus } H_{A1.Chol}: \mu_{ligelizumab} < \mu_{Placebo}$$

where  $\mu$  is the mean change from baseline in itch NRS following the pulse controlled ergometry test at week 12, negative value indicates improvement.

All primary and secondary endpoints will be tested against the respective alternative hypotheses in a closed testing procedure (Bretz et al 2009), so that the family-wise type I error will be controlled at 0.025 (one-sided) for each sub-type. The detailed testing strategy is provided in [Section 12.5](#).

### **12.4.3 Handling of remaining intercurrent events of primary estimand**

Participants who discontinue from study treatment early will be encouraged to stay in the study following the procedure described in [Section 9.1.1](#). These are considered as retrieved drop-out (RDO) participants.

For all three CINDU subtypes, symptomatic dermographism, cold urticaria, and cholinergic urticaria, the primary analysis will account for different intercurrent events as explained in the following:

- **Discontinuation of assigned study treatment either due to AE or lack of efficacy or use of prohibited medications:** Retrieved drop out (RDO) data collected after study treatment discontinuation will be used for analysis. If no RDO data was collected after study treatment permanent discontinuation, missing data for ligelizumab groups will be

multiply imputed based on information from the placebo, and under the MAR assumption for the placebo group.

- **Discontinuation of study treatment for the reasons other than AE or lack of efficacy or use of prohibited medications:** primary variable will be treated as missing and multiply imputed under the MAR assumption for all the groups.
- **Use of prohibited medications prior to Week 12 and not resulting in treatment discontinuation:** handled by treatment policy, data collected after the intercurrent event will be used as it is.
- **Missed treatment prior to Week 12 due to other non-human controlled emergency situations (e.g. COVID-19):** primary variable will be treated as missing and multiply imputed under the MAR assumption for all the groups.

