- **Treatment of interest:** ligelizumab or the placebo treatment (no further treatment for patients who discontinue treatment due to AE, lack of efficacy or intake of prohibited medications) with stable H1-antihistamines at local-approved doses as background medication + allowed rescue medication. The dose of the allowed background medication for CINDU must remain stable during the trial. Further details about the investigational treatment and control treatment are provided in [Section 6](#).
- **Handling of remaining intercurrent events:**
  1. Discontinuation of initial assigned study treatment prior to Week 12 due to adverse events (AE), use of prohibited medications or lack of efficacy (LoE): Participants who discontinue from study treatment early will be encouraged to stay in the study as detailed in [Section 9.1.1](#). Retrieved drop out (RDO) data collected after study treatment discontinuation will be used for analysis (treatment policy).
  2. Discontinuation of initial assigned study treatment prior to Week 12 due to reasons other than adverse events (AE), use of prohibited medications, or lack of efficacy

- (LoE): had participants taken the assigned treatment up to Week 12 (hypothetical strategy).
3. Use of prohibited medications prior to Week 12 and not result in treatment discontinuation: ignore (treatment policy).
  4. Missed treatment prior to Week 12 due to other non-human controlled emergency situations (e.g. COVID-19): had participants not missed treatment prior to Week 12 (hypothetical strategy).
- **The summary measure:**
    1. Symptomatic Dermographism: difference in mean change from baseline in Total Fric Score at Week 12 between treatments (ligelizumab 72 mg q4w vs placebo and ligelizumab 120 mg q4w vs placebo)
    2. Cold urticaria: difference in mean change from baseline of CTT at Week 12 between treatments (ligelizumab 72 mg q4w vs placebo and ligelizumab 120 mg q4w vs placebo)
    3. Cholinergic urticaria: difference in mean change from baseline in itch NRS in response to the pulse-controlled ergometry test at Week 12 between treatments (ligelizumab 120 mg q4w vs placebo)

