### **3 Study design**

#### **3.1 Study design**

This is a Phase III multicenter, randomized, double-blind, placebo-controlled study to demonstrate superiority of ligelizumab 72 mg and/or 120 mg sc q4w over placebo as an add-on therapy to H1-antihistamines at local-approved doses in adolescents and adults for the treatment of Chronic Inducible Urticaria (CINDU). The study will be approximately 40 weeks in duration with the primary endpoint assessed at Week 12. There are 3 subtypes of CINDU populations being assessed in three parallel cohorts; symptomatic dermographism, cold urticaria and cholinergic urticaria. The study consists of 3 distinct periods:

Screening period (Day - 28 to Day 0): Duration of up to 4 weeks in which participants who have given informed consent are assessed for eligibility.

Treatment period (24 weeks): There are 8 visits during this period. Participants will receive treatment at 6 visits (Week 0, Week 4, Week 8, Week 12, Week 16 and Week 20). No treatment will be given at Week 1 and Week 24 (End of Treatment visit). Provocation testing will be done at Week 0, Week 4, Week 8, Week 12 and Week 24.

Follow-up period (12 weeks): The participants should be seen in the clinic every 4 weeks until Week 36. There will be no study treatment administered at these visits; provocation testing will be done at Week 36 only.

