**Figure 3-1 Study design**

### 3.2 Provocation tests

**Important: Study treatment must NOT be administered before any provocation test.**

The procedure to perform the provocation tests are outlined in detail in the provocation test manual and should be followed.

Participants from the three subtypes should avoid exposure to triggers 24 hours before their provocation test.

For symptomatic dermographism and cold urticaria, participants must not have any CINDU related symptoms at the **provocation test site** for at least 24 hours prior to the provocation test. For cholinergic urticaria, participants with cholinergic urticaria are required to be symptom free before the start of the provocation test.

All participants must avoid taking any rescue medication in the 24 hours prior to the provocation test. It is recommended to keep at least 30 minutes between provocation test and drug administration.

For both cold urticaria and symptomatic dermographism participants, the provocation test will be applied to specific areas on the body e.g left volar forearm, upper back. The body area will be recorded in the eCRF (Electronic case report form). The body area must be free from inflammation, injuries, broken or infected skin and it is recommended that the same body part be used throughout the study. For cholinergic urticaria as the whole body is involved in the

provocation test, the different body areas where the hives appear will also be recorded in the eCRF.

In certain situations, the provocation test may be repeated as long as the participant has refrained from taking rescue medication in the 24 hours preceding the repeat provocation test.

For all three subtypes, if the provocation test was not performed correctly as per user instructions or if there were technical issues encountered during the provocation test or if the investigator suspects a false negative and the participant did not experience any symptoms, the test may be repeated. In this case, a minimum of 30 minutes is required between tests.

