#### 8.3.1 Provocation tests

Depending on the CINDU subtype, each participant will undergo provocation testing at the visits outlined in the Schedule of assessments (Table 8-1). Details on how to perform the provocation tests are outlined in the provocation test manual and must be followed. All provocation tests must be performed prior to administration of any study treatment. It is recommended to leave at least 30 minutes between the provocation test and drug administration. Each provocation test is evaluated 10 minutes after completion of provocation test where hives, itch, pain and burning are assessed.

The provocation test results will be reported in the eCRF.

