If discontinuation from study treatment by the participant occurs, the investigator should make a reasonable effort to understand the primary reason for the participant's discontinuation from study treatment and record this information. Always consider reasons which are related to safety and efficacy first.

Participants who discontinue from study treatment will be expected to perform the Week 24/EoT/TD assessments 4 weeks after their last dose and will be expected to perform all follow-up assessments (Week 28 to 36).

If the participant cannot or is unwilling to attend any visit(s), the site staff should maintain regular telephone contact with the participant, or with a person pre-designated by the participant. This telephone contact should preferably be done according to the study visit schedule.

For participants who wish to prematurely discontinue treatment prior to the primary endpoint (Week 12) for any reason, every effort should be made to have them continue study visits as per the assessment schedule, at least until Week 12.

After discontinuation from study treatment, at a minimum, in abbreviated visits, the following data should be collected at clinic visits or via telephone/email contact:

- New / concomitant treatments
- Adverse Events / Serious Adverse Events

The investigator must also contact the IRT to register the participant's discontinuation from study treatment.

If discontinuation occurs because treatment code has been broken, please refer to Emergency breaking of treatment code section.

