2.5.3 Handling of intercurrent events

For all three CINDU subtypes (i.e., symptomatic dermographism, cold urticaria, and cholinergic urticaria), the primary analysis for the primary estimand will account for different intercurrent events as explained in the following:

- **Discontinuation of assigned study treatment prior to Week 12 either for the reasons of AE, or lack of efficacy, or use of prohibited medications:** Retrieved drop out (RDO) data collected after study treatment discontinuation will be used for analysis. If provocation tests are performed at the EOT and/or the EOS visit, and the provocation test date(s) is within the +/- 4 weeks window of the date of the planned Week 12 visit, then the outcomes yield from the EOT or EOS provocation test, whichever is closer to the planned Week 12 date, will be considered as the RDO data for the primary endpoint. If no RDO data was collected after study treatment permanent discontinuation, missing data for ligelizumab groups will be multiply imputed based on information borrowed from the placebo, and under the MAR assumption for the placebo group (*Treatment policy*).
- **Discontinuation of study treatment prior to Week 12 for the reasons other than AE or lack of efficacy or use of prohibited medications:** primary variable will be replaced by the multiply imputed values under the MAR assumption for all the groups (*hypothetical strategy*).
- **Use of prohibited medications prior to Week 12 and not result in treatment discontinuation:** handled by treatment policy, data collected after the intercurrent event will be used as it is (*Treatment policy*).

- **Missed treatment prior to Week 12 due to other non-human controlled emergency situations (e.g. COVID-19):** primary variable will be replaced by the multiply imputed values under the MAR assumption for all the groups (*hypothetical strategy*).

2.5.3.1 Multiple intercurrent events occurring prior to Week 12

Multiple intercurrent events occurring prior to Week 12 will be handled by the hypothetical strategy only if all of them are classified as to be handled by the hypothetical strategy individually, in which case, data after the first intercurrent event will be replaced by multiply imputed values under the MAR assumption.

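### An observed Week 12 result is replaced by imputation after an other-reason stop, even when all three doses due before the Week 12 test were given

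*Protocol*

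**What the plan says.** **Estimand (Protocol 2.1).** The intercurrent event is described as "Discontinuation of initial assigned study treatment prior to Week 12 due to reasons other than adverse events (AE), use of prohibited medications", with inefficacy named as the third excepted reason. It is handled by a hypothetical strategy: the outcome "had participants taken the assigned treatment up to Week 12". SAP 1.2.1 agrees.

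**Analysis rule.** Protocol 12.4.3 states for this event that the "primary variable will be treated as missing and multiply imputed under the MAR assumption for all the groups". SAP 2.5.3 states that the "primary variable will be replaced by the multiply imputed values under the MAR assumption for all the groups". Data collected after stopping are used only when the reason was an adverse event, lack of efficacy or prohibited medication.

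**Dosing and test order.** Protocol 3.1 places doses at Weeks 0, 4, 8, 12, 16 and 20. Section 3.2 says "Study treatment must NOT be administered before any provocation test", and Section 8.3.1 repeats that "All provocation tests must be performed prior to administration of any study treatment".

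**Follow-up after stopping.** Protocol 9.1.1 says "Participants who discontinue from study treatment will be expected to perform the Week 24/EoT/TD assessments 4 weeks after their last dose". For stops before Week 12 it also asks sites to try to keep participants attending at least to Week 12, whatever the reason.

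**The concern.** A hypothetical strategy normally sets aside data after the event because they reflect the absence of treatment that the question supposes was given. That reason is missing here. If the Week 0, 4 and 8 doses were given, no dose that could influence the Week 12 test was missed. The protocol arranges to collect the result, and the analysis rule then replaces it with a model-based value.

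Two things are at stake. Some precision is lost. More importantly, the primary result leans on missing at random for people whose target outcome may have been observed, which is more than the estimand requires.

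**Working it through.** **1. Does the observed value answer the question?**

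- Doses due before the Week 12 test: Weeks 0, 4 and 8, which is three (Protocol 3.1).
- The Week 12 dose follows the Week 12 test (3.2 and 8.3.1), so it cannot affect the result.
- A participant who stops after the Week 8 dose, with none missed, has had 3 of 3 relevant doses.
- The assessment due 4 weeks after the last dose (9.1.1) falls at 8 + 4 = Week 12.

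The condition in Section 2.1 is met. Whether the phrase is taken to include the Week 12 dose makes no difference to the Week 12 outcome.

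**2. Does any rule keep the value?** Neither 12.4.3 nor SAP 2.5.3 makes an exception by doses received. SAP 2.5.3.1 applies the hypothetical strategy to several events only if all of them are hypothetical-strategy events. A participant who also had a treatment-policy event would therefore escape replacement, but one with only an other-reason stop would not.

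**3. The plan's own power figures.** These use a two-sample t-test, one-sided, with n per arm equal to N × (1 − 0.10) rounded down, df = 2n − 2 and noncentrality = difference / (SD × √(2/n)).

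| Cohort | Inputs (Protocol 12.8.1) | n per arm | Recomputed | Stated |
|---|---|---|---|---|
| Dermographism | 1.3, SD 1.7, α 0.0125 | 50 | 93.7% | 93.7% |
| Cold | 10, SD 8, α 0.0125 | 30 | 99.4% | >99% |
| Cholinergic | 1.65, SD 3.0, α 0.025 | 71 | 90.2% | 90.2% |

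For the cholinergic cohort the noncentrality is 1.65 / (3.0 × √(2/71)) = 3.277 on 140 df.

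**4. Illustrative size.** The documents do not give the number of participants who stop treatment for other reasons after the Week 8 dose and are still tested. As an assumption only: 10% stop before Week 12, spread evenly over three dosing intervals, half to all of them for other reasons, and all tested. The share is 10% × 1/3 × (0.5 to 1) = 1.7% to 3.3%.

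- Dermographism: 56 × share = 0.9 to 1.9 per arm
- Cold: 34 × share = 0.6 to 1.1 per arm
- Cholinergic: 79 × share = 1.3 to 2.6 per arm

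Adding the cholinergic results to 71 gives 72.3 to 73.6. Power is 91.0% at 73 per arm and 91.4% at 74, against 90.2% at 71.

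**5. Outer limit.** If the whole 10% were such participants, 7.9 results per cholinergic arm would be kept (n = 79) and power would be 93.0%. That requires every stop to fall after the Week 8 dose, for another reason, with the test done, so it marks the end of the range and is not an expectation.

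Steps 4 and 5 give imputed participants no information. Week 4 and Week 8 tests exist and could inform the imputation, so the gains are upper bounds.

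**The case against.** The strongest case against has five parts.

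- **The discontinuation date is undefined.** The glossary speaks only of the point at which treatment permanently stops. If that is dated by the first dose not given, a participant who has the first three doses and declines the Week 12 dose has not stopped before Week 12, and the value stands. This narrows the problem but does not remove it: someone who decides to stop, and is registered as stopping, between Weeks 8 and 12 is caught on the natural reading.
- **Such participants are not all equivalent to completers.** Unblinding requires discontinuation (9.1.1) and can fall under other reasons. Table 4-1 stresses blinding because itch severity is subjective, and itch NRS is the cholinergic primary endpoint. This stands, and the fix needs a guard.
- **The test may be missing or carry another label.** Section 9.1.1 expects the 4-week assessment, but the minimum data after stopping are only treatments and adverse events. SAP 2.1.1.3 assigns study week by visit name, and the ±4-week mapping of EOT/EOS tests to Week 12 appears only in the bullet for the other three reasons. This also stands.
- **The 10% is a study drop-out rate** (Protocol 5). People who leave the study before Week 12 have no Week 12 result to discard. The per-arm counts are therefore illustrations and not estimates from the plan.
- **Section 12.4.3 is not read alone.** Because it omits the limit to stops before Week 12 for this event, a reader might infer that it also discards Week 12 results of people who stop later. The documents do not support that: 12.4.1 refers the definition to 2.1, and both 2.1 and SAP 2.5.3 carry the limit. Only a wording mismatch remains.

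**Conclusion.** The point holds as a mismatch between estimand and analysis rule. For other-reason stops before Week 12, both documents replace the Week 12 value even when all three relevant doses were given and the test was done, although that value already answers the question in 2.1.

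The size is small. The number affected is not in the documents and is probably a few per arm at most. The cholinergic power gain is about one point at most (90.2% to 91.0–91.4%), assuming 10% evenly spread stops, half to all for other reasons, full testing and no information from imputed participants. A reader might infer bias or a material loss of power; neither is shown. The benefit lies in alignment and in less dependence on missing at random.

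Nor is a reported result affected. The SAP introduction and Section 4 state that no statistical analysis of the primary endpoints will be run after the early termination, and SAP 1.1.2 records only 3 participants completing Week 12. The weakness is in the planned method.

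**What to change.** In Protocol 12.4.3 and SAP 2.5.3:

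1. Apply the hypothetical strategy to an other-reason stop only when a dose due at Week 0, 4 or 8 was not given because of the discontinuation. This also removes the dependence on an undefined discontinuation date.
2. Otherwise use the observed Week 12 result, including an EoT/TD provocation test that falls in the Week 12 window. Extend the SAP's ±4-week mapping to this case, or set a tighter window. A tighter one fits better, since a test well after Week 12 would follow a lapse in treatment. If there is no such test, impute as now.
3. Keep imputation when the reason for stopping was unblinding.
4. Repeat in 12.4.3 that the event is discontinuation before Week 12, to match 2.1 and the SAP. This is alignment only.

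The cost is a few sentences in each document and a visit-mapping rule in the programming. No new data collection is needed.

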#### 12.4.4 Handling of missing values not related to intercurrent event

If the provocation testing is stopped due to any reason e.g participant discomfort, technical issues the data will be considered as missing.

